- 3) Patient results will be sent to the ordering provider within 2 weeks of test completion and return.

Patients with normal results will be sent a letter to repeat CRC screening in 3 years. Patients with abnormal results will be sent a letter encouraging follow up colonoscopy, and their primary care provider will be notified and requested to order colonoscopy. Patients with colonoscopy orders will receive usual care colonoscopy scheduling, preparation, and completion by the UCSDHS GI department. Notably, some clinicians at UCSDHS are already offering Cologuard as a usual care screening test.

2. Mailed fecal immunochemical test (FIT) outreach.

The control group to be tested in the pilot is mailed FIT outreach, a multi-component strategy found to have the largest effect size to improve CRC screening uptake compared to usual care.^{35,36} FIT is a USPSTF-recommended at-home screening test for blood in stool. Abnormal FIT results are followed up with a colonoscopy to identify and remove pre-cancerous polyps or diagnose early-stage CRC.³⁴ FIT test kits will be prepared at UCSD Health to be delivered to participants randomized to this study arm. Participants randomized to mailed FIT outreach will receive:

- 1) advanced notification (primer) via mail one week prior to receiving the FIT kit;
- 2) FIT kit normally offered at UCSDHS (Polymedco OC Light) with study information, invitation and instructions to complete FIT and how to opt-out; and
- 3) reminders via mail 14 days and 28 days after FIT kit receipt.

FIT kits will be mailed to UCSD Health System to undergo current usual care assay and reporting, based on the Polymedco OC Light criteria (the current test used within UCSDHS). Patients with normal results will be sent a letter to repeat CRC screening in a year. Patients with abnormal results will be sent a letter encouraging follow up colonoscopy, and their primary care provider will be notified and requested to order colonoscopy. Patients with colonoscopy orders will receive usual care colonoscopy scheduling, preparation, and completion by the UCSDHS GI department.

D. Outcome Measures and Rationale

1. Aim 1 Interview Constructs

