Using the UCSDHS EHR, we will conduct a query for a list of all potential participants who meet the eligibility criteria. We will use both Epic and Care Everywhere platforms to ascertain eligibility criteria for recruitment. Among the list of adults deemed eligible for recruitment, we will stratify individuals based on their EHR-documented race/ethnicity into one of five groups: Non-Hispanic White, Black, Hispanic, Asian/Pacific Islander, Other. From these groups, we will select a list of 20 individuals to be recruited. In sum, the 100 individuals will be comprised of 20 individuals selected at random from 5 self-reported racial/ethnic groups, with the intent that each racial/ethnic group will have 10 individuals represented in the mailed Cologuard outreach and mailed FIT outreach (each group makes up 20% of the sample in each arm). This will ensure equal balance of participants from each racial/ethnic group in each trial arm.

Eligible individuals will be mailed a postcard briefly describing the study and asking patients to scan a QR code if they are interested in participating. The QR code will take eligible individuals to eConsent forms within REDCap, where they will be provided with informed consent and HIPAA Authorization forms that will need to be completed to participate in the study. Electronically completed and signed informed consent and HIPAA authorization forms will be required prior to randomization. HIPAA Authorization is necessary to release relevant patient information to Exact Sciences, the company that will mail and implement the Cologuard test, should the participant be randomized to that group. Additionally, HIPAA Authorization ensures participant electronic health records may be examined to measure the study's outcomes of interest over the course of study follow-up.

If individuals decline participation or do not sign HIPAA authorization and informed consent documents, they will be replaced by another eligible individual from the same EHR-documented race/ethnicity grouping. After agreeing to participate, individuals within each race/ethnic group will

be assigned randomly to the mailed Cologuard outreach and mailed FIT outreach arms, such that an equal number of individuals from each group is included in each trial arm. Recruitment will continue until a sample size of 50 individuals per trial arm (mailed Cologuard outreach and mailed FIT outreach) who consent to participation in the study is achieved.

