The primary study endpoint is colorectal cancer (CRC) screening completion within 3 months of randomization. We plan to measure this using Healthcare Effectiveness Data and Information Set (HEDIS) documentation to inform our CRC screening uptake variable. This variable will incorporate CPT, Healthcare Common Procedural Coding System (HCPCS), and ICD-9/10 coding to identify FIT or guaiac fecal occult blood tests (CPT: 82270, 82274; HCPCS: G0328), flexible sigmoidoscopy (CPT: 45330-45335, 45337-45342, 45345-45347, 45349, 45350; HCPCS: G0104; ICD-9: 45.24), colonoscopy (*CPT/HCPCS codes mentioned in **Table 1***; ICD-9: 45.22, 45.23, 45.25, 45.42, 45.43), CT colonography (CPT: 74261-74263) and FIT-DNA (Cologuard) tests (CPT: 81528, HCPCS: G0464). We will also conduct manual EHR review to validate our HEDIS-defined algorithm. After the initial EHR query to define our study population, we will do manual EHR review two times during the follow-up period, once in the first month after study start to test the HEDIS-defined algorithm and a follow-up review in the second month after study start to validate the final algorithm. At the end of 3 months of study follow-up we will use the validated final algorithm to query for CRC screening completion.

B. Secondary Endpoints

Aim 2 Pilot Trial Secondary Outcomes

In the pilot trial, we will measure multiple outcomes to assess feasibility of a larger trial. We will measure the total number of participants who opt out of the pilot as a recruitment outcome. We will also measure the number of participants with undeliverable Cologuard or FIT kits, known as mail fail rate, as an intervention outcome. Among those with abnormal Cologuard or FIT, we will measure the proportion who are referred to colonoscopy and proportion who complete colonoscopy. We will measure the proportion who are referred to colonoscopy and the proportion who complete colonoscopy via manual EHR review of participants with abnormal Cologuard or

FIT results. We will conduct the manual EHR review 3 months, 6 months and 9 months after randomization, only among randomized study participants (those who provided signed HIPAA authorization and informed consent).

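### The primary outcome rests on a code query at the end of 3 months with no run-out, no qualifying date and no validation by arm, although the two tests report by different routes

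*Combined protocol and SAP*

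**What the plan says.** All references are to the combined protocol and SAP.

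- **Endpoint.** Study Outcome Measurements, A. Primary Endpoints, Aim 2: "The primary study endpoint is colorectal cancer (CRC) screening completion within 3 months of randomization". It is built from CPT, HCPCS and ICD codes. The code for Cologuard is on the list.
- **Capture.** Same section: "At the end of 3 months of study follow-up we will use the validated final algorithm to query for CRC screening completion". No interval is left for results to post. No text says whether collection, laboratory receipt, result or posting date counts.
- **Validation.** Same section: manual review takes place "once in the first month after study start to test the HEDIS-defined algorithm", followed by "a follow-up review in the second month after study start to validate the final algorithm". Both times run from study start, not from each randomization, and no check by arm is required.
- **Cologuard route.** Patient Population, A. Recruitment and Screening Strategy describes the outside firm as "the company that will mail and implement the Cologuard test". Intervention Regimens and Rationale, item 1, adds: "Patient results will be sent to the ordering provider within 2 weeks of test completion and return".
- **FIT route.** Intervention Regimens and Rationale, item 2: "FIT kits will be mailed to UCSD Health System to undergo current usual care assay and reporting". No turnaround time is given.
- **Later chart review.** Outcome Measures and Rationale (item 3) and B. Secondary Endpoints plan manual reviews at 3, 6 and 9 months, to track colonoscopy after an abnormal stool test. Stratification and Randomization, B. Blinding, mentions passive chart review to 9 months without linking it to the primary outcome.
- **Follow-up length.** Stratification and Randomization, A. Randomization, gives 6 months for the primary outcome. B. Blinding and the Primary Endpoints section give 3.

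**The concern.** A participant counts as screened only if the test leaves a recognised code in the record by the time of the query. A FIT is assayed and reported inside the health system. A Cologuard result starts at an outside laboratory, travels to the ordering provider, and must then reach a coded field by a step that the plan does not describe. A late or uncoded Cologuard result would be counted as not screened. If this happened more often than for FIT, the primary comparison would be biased against Cologuard.

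The stated validation may not reveal this. It ends in the second month after study start, while recruitment runs by postcard and opt-in until 50 per arm have consented, and it need not look at the arms separately. A normal Cologuard result that never became a code would also fall outside the 3-, 6- and 9-month reviews as described, because those concern abnormal results.

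The pilot is meant to inform the power and sample size of the larger trial, so a capture difference would carry forward into that design.

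**Working it through.** **Inputs from the documents.** There are 50 participants per arm. The FIT completion rate is 23%, and the target is a 15-point higher rate with Cologuard, hence 38% (E. Sample Size and Rationale). Results take up to 2 weeks after return. A primer goes out one week before the kit. Cologuard support lasts 2 months.

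**Inputs that are assumptions.** The share of Cologuard completions captured, the day the kit arrives, and the pattern of returns are assumed. Three months is taken as 91 days and two months as 61. FIT capture is set at 100% because no FIT turnaround is given.

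**Plan's own figure.** The plan gives no figure for capture or lag. The one design calculation beside these rates is 80% power for 38% vs 23%. With unpooled variance:

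- SE = √(0.23×0.77/50 + 0.38×0.62/50) = 0.091
- power = Φ(0.15/0.091 − 1.96) ≈ 38% (37% with pooled variance)

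The stated 80% does not reproduce. That is a separate matter; only the two rates are used below.

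**Step 1: effect of incomplete capture.** Observed difference = 0.38×s − 0.23, where s is the share of Cologuard completions captured.

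| s (assumed) | Observed Cologuard rate | Observed difference |
|---|---|---|
| 1.00 | 38.0% | 15.0 points |
| 0.90 | 34.2% | 11.2 points |
| 0.80 | 30.4% | 7.4 points |

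If both arms truly complete at 23%, s = 0.90 or 0.80 gives 23×s − 23 = −2.3 or −4.6 points. About 0.38×50 = 19 Cologuard completers are expected. Each one missed moves the arm rate by 1/50 = 2 points.

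**Step 2: lag alone.** Suppose the query ran on each participant's day 91 and every result took the full 14 days. Tests returned in the last 14 days of the window would then be missed.

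| Kit arrives | Uniform returns to day 91 | Returns stop 2 months after arrival |
|---|---|---|
| Day 7 | 14/84 = 17% | ends day 68: 0% |
| Day 14 | 14/77 = 18% | ends day 75: 0% |
| Day 21 | 14/70 = 20% | ends day 82: 5/61 = 8% |

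These are ceilings, because 2 weeks is the stated maximum. Any FIT lag would offset part of them.

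**Step 3: what the validation can see.** Take someone randomized on day 0 whose primer is mailed at once. The kit comes no earlier than day 7, and the result may take 14 days after return. A test returned on arrival might therefore not be reported until day 7 + 14 = 21, before any shipping or collection time. The month-1 review can cover only the fastest returns of the earliest enrollees. The month-2 review covers more, but it still cannot cover anyone enrolled later, nor the end of any participant's window.

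**Step 4: consequence for the next trial (illustration).** The number per arm for 80% power at two-sided 0.05, with pooled variance under the null, is 147 for 38% vs 23%. It is about 255 for 34.2% vs 23% and about 560 for 30.4% vs 23%.

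**The case against.** The strongest reply is that nothing shows Cologuard results are likely to be lost. They go to the study's own ordering provider. Normal and abnormal results each trigger a letter, so someone handles every processed result. Some clinicians in the system already use the test, and its code is in the algorithm. This stands: the gap is that these results are not named as an outcome source and their path to a code is not described. A reader might infer that under-capture will fall on Cologuard and favour FIT. The documents support only that it could.

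Other stronger readings also go too far:

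- **The query falls on exactly day 91 for everyone.** The text does not say whether it runs per participant or once for the cohort. One query after the last window closes would confine the lag problem to late enrollees. If the 6-month statement governs, the lag arithmetic changes altogether.
- **Few tests will exist by month 2.** No accrual timeline is given. For someone randomized at study start, with a kit on day 14 and uniform returns to day 91, (60 − 14)/77 = 60% of completions occur by day 60.
- **The month-1 and month-2 reviews are the only check.** The passive review to 9 months is not limited to abnormal results where it is mentioned. It is also not tied to the primary outcome, so its scope is unclear.

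Finally, this is a feasibility pilot, and the illustrated shifts of 3.8 and 7.6 points are smaller than the standard error of about 9 points. That lowers the severity. It does not remove the point, because a capture difference is a systematic error and would carry into the larger trial.

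**Conclusion.** The concern holds in limited form. The plan states a capture and validation rule that can count a late or uncoded Cologuard completion as not screened, does not require a check by arm, and sends the two tests' results by different routes. Capture can therefore differ by arm without the stated checks showing it.

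Neither the size nor the direction is established. The 11.2- and 7.4-point figures rest on assumed capture of 90% and 80% with FIT fully captured. The lag range of 0% to about 20% rests on assumed arrival days and return patterns, the full 2-week delay for every result, and a query on each participant's last day. What follows directly from the plan is that one missed result costs 2 points in a 50-person arm.

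This should be fixed, but in a feasibility pilot it does not invalidate the design.

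**What to change.** In Study Outcome Measurements, A. Primary Endpoints, Aim 2:

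1. Count a stool test by specimen collection date (or laboratory receipt date, if chosen and stated) falling within the primary window.
2. Run the query after a fixed run-out following each participant's window. It should be longer than the 2-week result time, for example 30 days.
3. Confirm the outcome for all 100 participants, in both arms, by one chart review after the run-out. Name as sources the Cologuard results sent to the ordering provider and the health system's FIT laboratory results. The Study Interventions section says only that Cologuard results go to providers, so align it with the section that names the ordering provider.
4. Report the code algorithm's sensitivity against this review, by arm, as a feasibility result. With about 19 and 0.23×50 ≈ 11.5 expected completers, it will be imprecise but useful to the larger trial.
5. Reconcile the 3-month window with the 6-month statement under A. Randomization.

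The month-1 and month-2 reviews may stay as an early check. The cost is about 100 short chart reviews by the existing team and a data cut roughly one month later.

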This study employs a mixed methods design to develop a CRC screening strategy for adults ages 45-49. First, our study will employ interviews of pilot trial participants and providers involved in CRC screening referral and coordination to qualitatively examine factors influencing CRC screening uptake. In parallel, we will conduct a pilot randomized controlled trial to compare a mailed multi-target stool DNA test (Cologuard) outreach strategy to mailed fecal immunochemical test (FIT) outreach. Results from our interviews and the pilot trial will inform a larger, fully powered trial of Cologuard outreach vs. mailed FIT outreach for CRC screening.

A. Study Rationale

We chose to pursue this mixed methods design to simultaneously learn about factors at the patient, provider and system levels that might influence CRC screening uptake and examine the potential acceptability of a mailed Cologuard outreach strategy compared to mailed FIT outreach. The trial will enable us to conduct a real-world examination of potential uptake of CRC screening among adults ages 45-49, where evidence regarding CRC screening is currently limited.

We choose to test the mailed Cologuard outreach strategy as the primary pilot intervention because of its demonstrated efficacy among adults ages 50-75, and potentially greater acceptability as a screening modality compared to other available tests.³³ The control group will receive mailed FIT outreach, a strategy proven effective at increasing CRC screening uptake among individuals not up to date with screening.^{34,35} This control arm reflects a proven screening outreach strategy that has been implemented in many settings, including at University of California San Diego Health System.

We acknowledge that some adults ages 45-49 might be more inclined to utilize other screening modalities, such as colonoscopy. Thus, we are measuring screening uptake as an outcome of our study, to include any potential screening modality used as covered by the USPSTF guidelines. Our decision to consider any potential screening modality uptake as completed

screening is based on the ultimate goal of the study to maximize screening among this newly eligible screening population.

B. Study Population and Rationale

Aim 1. Interviews

The specific inclusion criteria for Aim 1 are:

Patient Participants

- Adults ages 45-49.
- EHR documentation indicating the patient has an assigned primary care provider at UCSDHS
- ≥1 UCSDHS health visit within the last year

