In the pilot trial, we will measure multiple outcomes to assess feasibility of a larger trial. We will measure the total number of participants who opt out of participation in the pilot as a recruitment outcome. We will also measure the number of participants with undeliverable Cologuard or FIT kits, known as mail fail rate, as an intervention outcome. Number of individuals with kits that could not be processed due to collection issues (missing collection date, too much or too little sample) will be quantified for both groups. Among those with abnormal Cologuard or FIT, we will measure the proportion who are referred to colonoscopy and the proportion who complete colonoscopy via manual EHR review of participants with abnormal Cologuard or FIT results. We will conduct the manual EHR review at 3 months, 6 months, and 9 months post-randomization. If through the course of manual EHR review a patient is discovered not to have completed colonoscopy, the study team will contact the assigned primary care provider to alert them that the patient had an abnormal Cologuard or FIT and did not complete colonoscopy. The contact will be through a UCSD Epic staff message from the study team to the primary provider. If receipt of the message is not acknowledged after two staff messages, then the study team will contact the primary provider's assigned clinic staff via telephone to alert them that the patient has an abnormal Cologuard or FIT and has not received referral for colonoscopy.

E. Sample Size and Rationale

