However, the use of a standardized consent form aids in assuring that participants receive adequate and consistent information about the pilot trial and have consented to participate. The study investigator will provide written documentation that explains the study to the individual and present him or her with the detailed consent form to read and review. In some cases, this process may be initiated by telephone, such as for individuals who call the study investigator to learn more about the pilot trial. Telephone contact may only be initiated by the potential participant. While we will strongly encourage a face-to-face informed consent process, such a process for this type of study is not ideal, because it will less closely reflect the future state we are trying to mimic, in which the convenience of mail-based outreach can be used to facilitate participation in CRC screening. Thus, we propose a process whereby the informed consent

form and HIPAA Authorization form are provided via 1) an electronic eConsent form within REDCap. A postcard will be mailed to the potential participant's home, including a QR code where the potential participant may access, review, and sign the informed consent and HIPAA Authorization forms.

The components of the pilot trial will be clearly described, including the potential interventions participants could be exposed to, as well as the general intent of the study. The potential participant will be notified that randomization to the Cologuard intervention would lead to their name, medical record number, date of birth, sex, address, phone number, and health insurance information being shared with Exact Sciences to facilitate mailing of the Cologuard test and delivery of test results.

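### The pilot's only recruitment outcome is an undefined count of opt-outs, which does not fit opt-in recruitment and cannot be read as recruitment yield

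*Combined protocol and SAP*

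**What the plan says.** The recruitment outcome appears twice in nearly the same words. Study Outcome Measurements, B. Secondary Endpoints, has "We will measure the total number of participants who opt out of the pilot as a recruitment outcome". Summary of the Study Design, D. Outcome Measures and Rationale, item 3, has "We will measure the total number of participants who opt out of participation in the pilot as a recruitment outcome". It is one of several secondary feasibility outcomes and the only one labelled a recruitment outcome.

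The recruitment process is set out under Patient Population, A. Recruitment and Screening Strategy (Aim 2), and again under Stratification and Randomization, A. Randomization:

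- Eligible people are mailed a postcard "asking patients to scan a QR code if they are interested in participating".
- "Electronically completed and signed informed consent and HIPAA authorization forms will be required prior to randomization".
- "If individuals decline participation or do not sign HIPAA authorization and informed consent documents, they will be replaced by another eligible individual" from the same race/ethnicity group, and recruitment runs until each arm has 50 consenting people.
- The Aim 2 consent section adds: "Telephone contact may only be initiated by the potential participant".

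After randomization, the FIT kit comes "with study information, invitation and instructions to complete FIT and how to opt-out" (C. Intervention Regimens and Rationale, item 2, and similarly under Study Interventions). The component lists for the Cologuard arm have no such item. The consent information for both arms does say that participation is voluntary and that a person may withdraw without penalty.

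Study Rationale describes the aim this way: "The trial will enable us to conduct a real-world examination of potential uptake of CRC screening among adults ages 45-49".

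**The concern.** In an opt-in process the usual way not to join is to do nothing. The pilot describes no route for refusing at the postcard stage, and the team may not telephone people who stay silent. A count of opt-outs could therefore miss most of those who were invited and did not join.

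The purpose of Aim 2 is to establish whether a larger trial is feasible. For that, the team needs to know how many people must be invited to obtain one consent. It needs this by race/ethnicity group as well, because minimizing disparities is part of the primary objective. Filling every group to 20 makes the final sample look balanced however unequal the response was. Without yield, a reader also cannot judge how far uptake among people who answered a postcard and signed two forms carries over to the wider eligible population.

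**Working it through.** The documents state no expected opt-out count, response rate or consent rate, so there is no recruitment figure to reproduce. The check is whether the planned count determines yield.

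**Inputs from the documents.** Enrolment is 100 in total and 20 per race/ethnicity group.

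**Assumptions.** The consent rate per postcard, *c*, runs from 2% to 40%. The share of non-consenters who actively decline, *e*, is varied from 0% to 100%.

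**Formulas.**

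- Postcards: M = 100 / c
- Opt-outs counted: e × (M − 100)
- Yield a reader would infer from the count alone: 100 / (100 + opt-outs)

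| c (assumed) | Postcards M | Opt-outs, e = 0% | Opt-outs, e = 5% | Inferred yield, e = 5% | Opt-outs, e = 100% | Inferred yield, e = 100% |
|---|---|---|---|---|---|---|
| 2% | 5,000 | 0 | 245 | 29% | 4,900 | 2% |
| 5% | 2,000 | 0 | 95 | 51% | 1,900 | 5% |
| 10% | 1,000 | 0 | 45 | 69% | 900 | 10% |
| 20% | 500 | 0 | 20 | 83% | 400 | 20% |
| 40% | 250 | 0 | 8 | 93% | 150 | 40% |

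Three things follow.

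1. If nobody actively declines (e = 0%), the count is 0 and the inferred yield is 100% at every true yield.
2. Similar counts fit quite different yields. With c = 10% and e = 5% there are 0.05 × 900 = 45 opt-outs. With c = 20% and e = 10% there are 0.10 × 400 = 40.
3. Only if everyone invited who did not sign is counted (e = 100%) does the inferred yield equal the true one.

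**By stratum.** Postcards per group = 20 / c. A group yielding 2% needs 20 / 0.02 = 1,000 postcards, and a group yielding 20% needs 20 / 0.20 = 100. Both end with 20 people. The planned outcome is a total, so it would not show this tenfold difference.

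**Who could be counted.** The text allows at least three readings: every invited person who does not sign, only those who actively refuse, or enrolled people who later leave, for instance through the FIT kit instruction. The third is withdrawal after randomization and says nothing about recruitment. The plan does not choose among them.

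**The case against.** The strongest reply is that the count may be perfectly sound. *Opt out* is undefined, and usage elsewhere is loose: the Aim 1 recruitment text describes interviewees as people who have not opted out, although they must book their own slot. (The Aim 1 consent text uses the term more actively, so usage is mixed.) If the team counts everyone who declines or does not sign, overall yield follows, because enrolment is fixed at 100. That stands. A reader might infer that the reported figure will be wrong, and the documents do not support that. They show that it is undefined and has no stated denominator.

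A second tempting inference is that opt-outs will be counted, or prompted, in the FIT arm only. The outcome is a total with no restriction by arm, both arms are told at consent that they may withdraw, and the content of the advance mailing is not described for either arm. The FIT wording might also refer to outreach or reminders rather than to the study. What remains is a question about the inserts.

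Third, replacement within strata should generate the mailing numbers anyway, so the information need not be lost. That is fair, but the plan does not commit to reporting them. The planned mail-failure outcome concerns kits, not postcards.

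Finally, no section says that uptake among volunteers will be presented as uptake among everyone invited. The real-world phrase comes from a rationale sentence, and the primary endpoint is already measured from randomization.

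**Conclusion.** The point holds as a mismatch between the stated recruitment outcome and the plan's own recruitment process. As written, the count does not determine recruitment yield, overall or by race/ethnicity group, and the fixed sample size cannot supply it. This deserves correction because Aim 2 exists to judge the feasibility of a larger trial, but it affects one secondary outcome and leaves the primary comparison untouched.

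The size cannot be stated from the documents. The 20-fold spread in postcards (5,000 versus 250) depends entirely on the assumed yields of 2% to 40%. The gap between inferred and true yield depends on the assumed share of active refusals and vanishes if all non-signers are counted. The documents do not establish that the figure will be wrong, that opt-outs will be tallied in one arm only, or that the next trial's recruitment pool will be misjudged.

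**What to change.** In both places where the recruitment outcome is stated, replace it with consent yield: people who consented divided by postcards mailed and not returned undeliverable, with a 95% CI, overall and per race/ethnicity stratum. Report separately the undeliverable postcards, no response, active decline, and forms started but not signed. State that 3-month uptake applies to consented volunteers.

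The precision would be useful. At an assumed 10% yield, the 95% half-width is 1.96 × √(0.1 × 0.9 / 1,000) = 1.9 percentage points overall and 1.96 × √(0.1 × 0.9 / 200) = 4.2 points in a stratum of 20 consents from 200 postcards.

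Report withdrawals after randomization by arm, apart from recruitment. Confirm that the opt-out or withdrawal information sent after randomization is the same in both arms, since only the FIT kit contents mention it.

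The cost is a mailing log kept by stratum and a minor check of the inserts. Race/ethnicity and mailing address are already recorded for recruitment, and no extra patients are needed.
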